
outcomes and data post-transplant will be compared between Arm 1 and Arm 2 where a) any study drug (G/P) related severe treatment emergent adverse events are included as a clinical outcome for Arm 1 and b) all events of treatment emergent Grade ≥ 3 laboratory values and severe G/P-related treatment emergent adverse events are included as clinical outcomes for Arm 1.
 
4) To compare time to deceased donor kidney transplantation among all patients who enrolled in this MYTHIC trial to transplant candidates from the Organ Procurement and Transplantation Network (OPTN) database; MYTHIC participants will be matched 1:3 to OPTN patients on demographics and characteristics known to influence waiting time including waiting list priority, blood group, geographic region, and sensitization.

Investigators: Multi-center, names on file with sponsor

Study Sites: Up to 7 sites

Study Population: HCV-negative subjects wait-listed for a kidney transplant

Number of Subjects to be Enrolled: Up to 90, including a target number of 30 kidney transplantation events from study eligible HCV RNA-positive kidney donors.

Methodology:
 
This is an open-label, multi-center, two-arm study to evaluate the efficacy and safety of fixed-dose combination tablets of glecaprevir/pibrentasvir (G/P) in HCV-negative subjects who consent to receive a kidney transplant from an HCV RNA-positive deceased kidney donor. 90 subjects will be consented for trial participation, out of whom 30 subjects at up to 7 sites are planned to receive an HCV RNA-positive kidney meeting study criteria and will be enrolled into a post-transplant treatment arm (Arm 1) receiving open-label G/P for 8 weeks post-transplant. The remaining enrolled subjects including those who do not receive a kidney meeting study criteria from an HCV RNA-positive donor will be followed in Arm 2 for the minimum duration of 1 year post-enrollment. Arm 2 includes subjects who do not receive a kidney at one of the study sites or who receive a standard of care kidney transplant (Arm 2B5 patients will be censored at the time of transplant at a non-study site). For subjects enrolled in Arm 1 of the study, the

first dose of G/P will be given as early as 3 days post-transplant. Patients must be out of the ICU, able to eat and drink, and take oral medications, so that G/P treatment can be safely initiated orally as judged by the site investigator.

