For subjects of Arm 1 and Arm 2A who become HCV infected, we will collect additional clinical outcomes of sclerosing cholestatic hepatitis and extrahepatic manifestations of HCV.

In additional analyses, G/P treatment-related severe adverse events, and G/P treatment-emergent Grade ≥ 3 laboratory values will be counted as clinical outcomes for subjects in Arm 1.

4. Additional allograft function outcomes for subjects post-transplant: mean eGFR over time and proteinuria.
5. Time to deceased donor kidney transplantation will be compared between all patients who enrolled in this MYTHIC trial and transplant candidates from the Organ Procurement and Transplantation Network (OPTN) database using a Cox

proportional hazards model; MYTHIC participants will be matched 1:3 to OPTN patients on demographics and characteristics known to influence waiting time including waiting list priority, blood group, geographic region, and sensitization.

6. In addition, for subjects in study Arm 2A receiving HCV RNA-negative/HCV Ab-positive kidneys, the rate of HCV transmission will be summarized.

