4.2 Secondary Objectives

The secondary objectives are:

- 1) Among all subjects enrolled in the study, to describe time to kidney transplant and cumulative incidence of each type of transplant: a study-eligible HCV RNA-positive kidney (Arm 1), a study-eligible HCV RNA-negative/HCV antibody-positive kidney (Arm 2A), or a kidney transplant performed as part of standard of care treatment (Arm 2B).

2) To describe clinical outcomes while on the waitlist after consent (Serious Adverse events [SAEs], delisting from waitlist, death) between those who receive a study-eligible HCV RNA-positive kidney (Arm 1) and in subjects consented for this study who do not receive a study-eligible kidney transplant from an HCV RNA-positive donor (all Arm 2 subjects) overall and with breakdown by the 3 categories of Arm 2 as below:

A: subjects who receive a kidney from a study-eligible HCV RNA-negative/HCV Ab-positive donor

B: subjects who receive a standard of care kidney transplant

C: subjects who were not transplanted within 1 year of consent

Hereafter, these categories will be referred to as Arms 2A, 2B and 2C.

A “standard of care” transplant will be defined as any of the following kidney transplants: a deceased donor HCV RNA-positive kidney transplant that did not meet donor criteria for Arm 1 or HCV RNA-positive kidney transplant that place after last transplant allowed for Arm 1 but met criteria for Arm 1 inclusion (2B1); a deceased donor HCV RNA-negative/HCV Ab-positive kidney transplant that either did not meet donor criteria or took place > 6 months after the last Arm 1 transplant (2B2); a deceased donor HCV RNA-negative/HCV Ab-negative transplant at a MYTHIC clinical site (2B3); any living donor kidney transplant at a MYTHIC clinical site (2B4); or any kidney transplant at a different center than the 7 clinical sites (2B5).

In addition, to compare the total number of inpatient hospital days while on the waitlist and after study consent in those who did receive a study eligible HCV RNA-positive kidney (Arm 1) vs total inpatient hospital days in those who did not (Arm 2) overall and with breakdown by the 3 categories of Arm 2 (2A, 2B and 2C).

3) To describe clinical outcomes and data post-transplant (death, graft failure, acute allograft rejection, delayed graft function, estimated glomerular filtration rate [eGFR], proteinuria, ALT elevation > 5 times the upper limit of normal (ULN), SAEs)

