8.1.4 Secondary Clinical Outcomes

Secondary clinical outcome analyses will be performed for subjects prior to kidney transplant in both Arms 1 and 2, and post kidney transplant for those who receive a kidney transplant in Arms 1 and 2. For details on safety reporting and periods of safety reporting see section 6.1.4.

The cumulative incidence function curves of time to kidney transplant will be created for each type of kidney transplant (Arms 1, 2A, 2B), and cumulative incidence and standard error (SE) will be calculated for each type of kidney transplant.

An exploratory analysis will create cumulative incidence function curves of time to kidney transplant for the subgroups of Arm 2B if sufficient subjects are enrolled in Arm 2B.

The number and percentage of subjects with clinical outcomes while on waitlist and after study consent (SAEs, delisting from waitlist, death) among subjects who receive an HCV RNA-positive kidney (Arm 1) and among those subjects who do not receive an HCV RNA-positive kidney (all Arm 2 subjects) overall and with breakdown by category of Arm 2 (2A, 2B, 2C). In addition, the total number of inpatient hospital days while on waitlist in those who did receive an HCV RNA-positive kidney (Arm 1) and total inpatient hospital days in those who did not (Arm 2) overall and with breakdown by category of Arm 2 will be summarized descriptively with mean, median, standard deviation (SD), minimum and maximum.

We will match MYTHIC trial participants 1:3 to comparators derived from the Organ Procurement and Transplantation Network database. Matching will be based on demographics and baseline characteristics known to influence waiting time, including waiting list priority, blood group, geographic region, and sensitization. A comparison of time to kidney transplantation between the kidney transplant candidates enrolled in the MYTHIC trial and OPTN comparators will be performed using a Cox proportional hazards model.

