8.2 Determination of Sample Size

This study is primarily designed to demonstrate feasibility and to generate preliminary data related to cure rates (defined as SVR₁₂) from treating donor-derived HCV infection post kidney transplantation using G/P. For this reason, the sample size was not determined with reference to power to detect differences between groups for the primary objective. The lower bound of a one-sided 95% confidence interval using the Wilson's score method, for various SVR₁₂ rates with a total sample size of 30 subjects are provided in Table 10.

Table 10: Estimated Lower Bound for 95% Confidence Interval for Cure Rate Based on Observed Number of Cures

Sample Size	No. of Observed Cures	Observed Cure Rate	Lower Bound for 95% CI of Cure (Wilson's Score)
30	30	100.0%	93.8%
30	29	96.7%	85.4%
30	28	93.3%	81.0%
30	27	90.0%	76.9%
30	26	86.7%	73.0%

As a secondary objective, we will compare time to kidney transplantation between the estimated 75 - 90 kidney transplant candidates enrolled in this trial with 225-270 matched kidney transplant candidates from the OPTN list (1:3 match). We estimate that at least 40

patients (44%) of 90 enrolled patients will undergo kidney transplantation versus 20% (or less) of comparators from OPTN list during an estimated 6 months of follow-up, with 80% power to detect a difference between groups.

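### Section 8.2 states 80% power where its own inputs give about 96–99%, and the analysis text for the registry comparison drops objective 4's deceased-donor restriction

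*Protocol*

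**What the plan says.** Protocol 8.2 gives one power statement for a between-group comparison. It says "we will compare time to kidney transplantation between the estimated 75 - 90 kidney transplant candidates enrolled in this trial" and 225–270 controls matched 1:3. The expected participant count is 40 or more, and the rates are put as "patients (44%) of 90 enrolled patients will undergo kidney transplantation versus 20% (or less) of comparators from OPTN list". The time frame and the power claim come next in that sentence: "during an estimated 6 months of follow-up, with 80% power to detect a difference between groups". It names no test, hazard ratio or loss rate. Section 8.1 sets a two-sided alpha of 0.05, and 8.1.4 names a Cox model.

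The event is described in two ways:

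- **Deceased donor only.** Secondary objective 4 (synopsis and 4.2) reads "To compare time to deceased donor kidney transplantation among all patients who enrolled in this MYTHIC trial". Synopsis endpoint 5 reads "Time to deceased donor kidney transplantation will be compared between all patients who enrolled in this MYTHIC trial".
- **Donor type not restricted.** Section 8.1.4 reads "A comparison of time to kidney transplantation between the kidney transplant candidates enrolled in the MYTHIC trial and OPTN comparators". Section 8.2 uses the same unrestricted term. Draft SAP Part 8 lists kidney transplant as the outcome and fits its prognostic score with KT as the event.

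On matching, 8.1.4 says "We will match MYTHIC trial participants 1:3 to comparators derived from the Organ Procurement and Transplantation Network database", while draft SAP Part 8(a) uses 1:5 matching to SRTR controls.

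**The concern.** Two separate things look wrong.

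First, a difference of 24 percentage points with 300 to 360 people should give far more than 80% power. A reader cannot tell which test, rates or losses lie behind the stated figure.

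Second, an analyst working from 8.1.4 or SAP Part 8 would analyse a different event from the one in objective 4. Living-donor transplants can occur on both sides. Arm 2B4 exists to record them among participants, and nothing removes them among controls. Inclusion criterion 5 requires that participants have no available compatible living donor at enrolment. No matching rule applies that to controls, and the matching factors named in 8.1.4 do not include it. If controls receive living-donor kidneys more often, counting those transplants would shrink the apparent gain in access to transplantation. It also means that the protocol gives no power figure for the event in objective 4.

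**Working it through.** **Inputs.** p1 = 40/90 = 0.444 and p2 = 0.20 (8.2). Group sizes are 90:270 and 75:225 (8.2). Alpha is 0.05 two-sided (8.1), so z = 1.96.

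**Two proportions, pooled null variance:** power = Φ[(p1 − p2 − 1.96·se0)/se1].

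- 90:270: pooled rate = (40 + 54)/360 = 0.261; se0 = √[0.261 × 0.739 × (1/90 + 1/270)] = 0.0535; se1 = √[0.444 × 0.556/90 + 0.20 × 0.80/270] = 0.0578. The argument is (0.2444 − 0.1048)/0.0578 = 2.42, so power is 99.2%.
- 75:225: se0 = 0.0586, se1 = 0.0633. The argument is 2.05, so power is 98.0%.

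**Schoenfeld, for a Cox or log-rank comparison:** HR = ln(1 − p1)/ln(1 − p2) = ln(0.556)/ln(0.80) = 2.63, ln HR = 0.968; power = Φ[√(D × ¼ × ¾) × ln HR − 1.96].

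- 90:270: D = 40 + 54 = 94; 4.198 × 0.968 − 1.96 = 2.11, so power is 98.2%.
- 75:225: D = 78.3; 3.832 × 0.968 − 1.96 = 1.75, so power is 96.0%.

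**Attempts to reproduce 80%:**

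| Groups | Two proportions | Schoenfeld |
|---|---|---|
| 90:270 | 99.2% | 98.2% |
| 75:225 | 98.0% | 96.0% |
| 90:450 (SAP ratio) | 99.6% | 98.4% |
| 75:375 (SAP ratio) | 98.8% | 96.4% |
| 90:90 | 94.6% | 95.8% |
| 75:75 | 90.1% | 92.0% |

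A simulated log-rank (Cox score) test stratified by matched set gives 99.2% (90 at 1:3) and 97.6% (75 at 1:3). At alpha 0.01 the two-proportion formula still gives 93–97%. Losing half of both groups, which 8.2 does not mention, brings that formula to about 82% (from 75:225) or 88% (from 90:270).

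**What 80% would mean.** With controls at 20% and a 1:3 match, 80% power corresponds to a participant rate of 34.8% (90) or 36.4% (75) by two proportions, and 36.1% or 37.8% by Schoenfeld. For 44% against 20%, about 36 against 108 people would suffice.

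**The event.** The two terms are not used interchangeably. Objective 1 is "to describe time to kidney transplant and cumulative incidence of each type of transplant" and covers Arm 2B, which includes living-donor 2B4. Objective 4 adds the deceased-donor restriction. SAP Part 5 uses KT for Arm 2A–2B transplants, so in the SAP's own usage KT includes living-donor kidneys.

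**Power for the deceased-donor event.** The documents give no split by donor type, so every rate below is an assumption. Entries are two proportions / Schoenfeld.

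| Assumed deceased-donor rates | 90:270 | 75:225 |
|---|---|---|
| 20% of events removed from both groups (32/90 vs 16%) | 96.3% / 93.5% | 93.0% / 88.7% |
| 25% removed from both (30/90 vs 15%) | 94.9% / 91.4% | 91.0% / 85.9% |
| 10% removed from participants only (36/90 vs 20%) | 95.5% / 92.5% | 91.8% / 87.4% |
| 25% removed from participants only (30/90 vs 20%) | 72.1% / 65.9% | 64.7% / 58.1% |

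**The case against.** **The power figure.** Section 8.2 describes a feasibility study and says that power did not determine the sample size for the primary objective. Section 5.1.5 ends enrolment after 30 Arm 1 transplants. The 80% therefore sizes nothing, and it errs on the safe side. The expected counts are worded as bounds (at least 40; 20% or less), so 80% might be meant as a floor. All of this limits the weight of the point. It does not rescue the figure: both bounds push power higher, and 8.2 mentions neither a floor nor a smaller target difference.

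**The event.** The wording in 8.1.4 and 8.2 may be shorthand, since 8.2 introduces the comparison as a secondary objective and objective 4 is clear. That is possible, but the contrast with objective 1 and the SAP's use of KT mean that shorthand cannot be assumed. Nor do the documents say how living-donor transplants are treated in this comparison.

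**Stronger readings to avoid.** A reader might infer that the deceased-donor comparison is underpowered. That would require taking living-donor events out of the participants while leaving controls at 20%, which is a figure for any transplant. It also sits badly with the argument that controls may have more such events. The 30 targeted Arm 1 transplants are all from deceased donors, and participants have no available living donor at entry, so a large living-donor share among the expected 40 looks unlikely. A reader might also infer that the trial is mis-sized or that the comparison is certainly biased. The documents support neither.

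**Conclusion.** The 80% is wrong as written for the event and rates that 8.2 gives. The correct figure is about 96–99% (98.0–99.2% by two proportions, 96.0–98.2% by Schoenfeld). The error is conservative, confined to a secondary comparison, and has no effect on the sample size or on the SVR12 analysis.

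The event mismatch is real and matters more. As written, 8.1.4 and SAP Part 8 would count living-donor transplants, which objective 4 excludes. Any resulting bias would plausibly run toward no benefit, if controls receive living-donor kidneys more often. Its size cannot be derived from the documents.

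Power for the deceased-donor event is unstated, not shown to be low. If 20–25% of events are removed from both groups it stays at about 86–96%. Among the cases above, it falls below 80% only where deceased-donor transplants among participants drop well below 40 while controls stay at 20%. The correction should be made, and it is cheap.

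**What to change.** 1. In 8.1.4, 8.2 and SAP Part 8(a) and 8(b), define the event as deceased-donor kidney transplantation, as objective 4 does. Fit the prognostic score to the same event.
2. State whether a living-donor transplant is censored or treated as a competing event in this comparison. SAP Part 4 already treats other transplant types as competing risks.
3. Re-estimate the 6-month deceased-donor rates in both groups and restate power in 8.2, naming the test and the matching ratio to be used (1:3 or 1:5). If 44% against 20% for any transplant is kept, give about 96–99% for that event and do not carry it over to the deceased-donor event.
4. Align the ratio and the named registry between protocol and SAP. The reference to 9(a) in SAP Part 8(b) is a clerical slip for 8(a).

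The cost is wording in two protocol sections and one SAP part, two re-estimated rates and one recalculation. No additional trial data are needed.

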8.3 Assignment of Participants to Study Arms: Methods

This is a two-arm study. All eligible subjects who entered the study will be observed. Observed subjects who accept a study-eligible HCV RNA-positive kidney allograft offer will be assigned to the G/P treatment Arm 1 and followed in that Arm up until 1 year post-transplant. All other enrolled study subjects will remain in Arm 2 of the study (see Figure 1A).

9.0 Ethics

9.1 Independent Ethics Committee (IEC) or Institutional Review Board (IRB)

Good Clinical Practice (GCP) requires that the clinical protocol, any protocol amendments, the MAVYRET USPI,¹⁰ the informed consent and all other forms of subject information related to the study (e.g., advertisements used to recruit subjects) and any other necessary documents be reviewed by an IEC/IRB. The IEC/IRB at each site will review the ethical, scientific and medical appropriateness of the study before it is conducted. IEC/IRB approval of the protocol, informed consent and subject information and/or advertising, as relevant, will be obtained prior to the authorization of drug shipment to a study site.

Any amendments to the protocol will require IEC/IRB approval prior to implementation of any changes made to the study design. The investigator will be required to submit, maintain and archive study essential documents according to ICH GCP.

Any serious adverse events that meet the reporting criteria, as dictated by local regulations, will be reported to both responsible Ethics Committees and Regulatory Agencies, as required by local regulations. During the conduct of the study, the investigator should promptly provide written reports (e.g., ICH Expedited Reports, and any additional reports

required by local regulations) to the IEC/IRB of any changes that affect the conduct of the study and/or increase the risk to subjects. Written documentation of the submission to the IEC/IRB should also be provided to the sponsor

9.2 Ethical Conduct of the Study

The study will be conducted in accordance with the protocol, International Conference on Harmonization (ICH) guidelines, applicable regulations and guidelines governing clinical study conduct and the ethical principles that have their origin in the Declaration of Helsinki. Responsibilities of the clinical investigator are specified in [Appendix A](#).

9.2.1 Ethics Analysis

The main ethical considerations in this trial are non-maleficence, respect for persons, and autonomy. Our selection criteria are designed to select subjects who are at substantial risk of death and health complications because of end-stage renal disease and chronic dialysis treatment. Transplantation with a HCV RNA-positive kidney and then treatment for HCV also involve risks, but it is plausible that survival and quality of life will still improve after transplantation compared to the alternative of additional years on dialysis. Our informed consent procedures are designed to enable individuals to make decisions that are consistent with their values. We will enumerate the many possible risks and plausible benefits. The processes of informed consent in this study will be conducted so that patients can ask questions, confer with their primary nephrologists and develop a full understanding of the trial procedures and risks, all of which is consistent with respect for persons. Lastly, subjects in the trial will retain the ability to consider organ offers and decide whether to accept an organ based on their own judgment about the value of that particular organ and after getting advice from their transplant team.

9.3 Subject Information and Consent

The processes of informed consent in this study are designed to give potential participants several opportunities to learn about HCV, the study and to understand risks and benefits. *As*

described in section **5.1.3 Screening**, study staff will discuss the study during an initial phone call, a subsequent educational session and finally during the informed consent session when subjects will have the opportunity to sign the informed consent document.

The investigator or his/her representative will explain the nature of the study to the subject, and answer all questions regarding this study. Prior to any study-related screening procedures being performed on the subject, the informed consent statement will be reviewed and signed and dated by the subject, the person who administered the informed consent, and any other signatories according to local requirements. A signed copy of the informed consent form will be given to the subject and the original will be placed in the subject's medical record. An entry must also be made in the subject's dated source documents to confirm that informed consent was obtained prior to any study-related procedures and that the subject received a signed copy.

9.4 Potential Risks and Benefits

9.4.1 Risks of Study Procedures

There are several areas of potential risk in this study. We will obtain several blood samples from each subject. There is a risk of bruising, hematoma, and infection after phlebotomy, which are possible but not considered serious AEs. Fainting may occur, which is unlikely but considered a serious AE. The removal of <70 cc of blood every 1-4 weeks during the 40-week post-transplant period is a potential risk; however this amount is routinely taken from subjects for clinical indications without adverse effect. Study medications will be delayed until after phlebotomy on each study day.

Because we may store subjects' blood samples, there may be confidentiality risks associated with the storage and analysis of those samples or the information resulting from the analysis of those samples. Samples may be used for genetic testing. Under some circumstances, it can be a risk for genetic information to be known. To help ensure confidentiality, samples will be coded and stored in a secured facility. While situations

cannot be foreseen where potentially sensitive genetic information is revealed or where people who should not have this information could obtain it (representing a loss of confidentiality), however, it is possible that presently unforeseen situations may arise where this could happen.

The risk of undergoing screening includes potential identification of new health problems that subjects were unaware of. If we discover new health problems, we will answer subjects' questions and try to arrange appropriate treatment if any is needed. If new health problems are discovered, it is possible that subjects would not be able to enter this study. It is also possible that subjects would no longer be eligible for kidney transplantation based on the results.

The risks associated with a Fibroscan are that the probe used on the abdomen during the Fibroscan may lead to mild soreness in the area for about a day.

The risks of any kidney transplant surgery include blood loss, infections, and deep vein thrombosis. There are also risks related to immunosuppression and standard anti-infective therapy. The risks of any kidney transplant also include primary graft non-function, delayed graft function, acute rejection, and death. Re-admissions within 30 days after a kidney transplant are expected in approximately 40% of patients.

There may also be a small risk of developing Focal and Segmental Glomerulosclerosis (FSGS) after receiving a kidney from HCV-RNA-positive donor and/or being treated for HCV after transplantation. However, this condition can also develop in patients who do not have HCV. There have been case reports of FSGS among patients receiving treatment for HCV after kidney and liver transplantation. It is possible that such cases were related to HCV treatment. After transplant, we will monitor all patients for FSGS and similar conditions by checking proteinuria at every study visit post-transplant.

There may also be a small risk of developing symptoms of acute HCV infection, or extrahepatic manifestations of HCV infection if the start of HCV treatment is delayed. After transplant, we will monitor all patients and will initiate HCV treatment as early as feasible on or after day 3 post-transplant.

Taking part in a research study may cause psychological distress or excess worry. A subject may experience discomfort if asked questions about the subject's medical history that the subject deems to be private.

